7. STUDY POPULATION

7.1 Eligibility criteria

All patients with FPSI will be included in this study irrespective of age, gender, degree of hyperlaxity, or duration of symptoms. Exclusion criteria focus on structural anomalies (static posterior migration, connective tissue diseases, degenerative joint diseases, structural defects) and other pathologies (multidirectional instability, neurological disorder or nerve injuries, existing pain syndrome, medical contraindication to EMS treatment) hindering, impeding, or prohibiting the complete administration of the control or experimental intervention. Additionally, patients with previous participation in a pathology-targeted standardized EMS or physiotherapy protocol are excluded in order to avoid patient's potential unwillingness to participate in or preformed mindset towards an intervention that they previously tried already without success. This combination of inclusion and exclusion criteria seems adequate to create a homogeneous group of study participants that still represents the typical characteristics of the majority of patients suffering from FPSI.

Participants fulfilling all of the following inclusion criteria are eligible for the study:

- Non-controllable positional functional posterior shoulder instability
- Informed Consent as documented by signature

The presence of any one of the following exclusion criteria will lead to exclusion of the participant:

- multidirectional instability
- static posterior instability/migration
- connective tissue disease
- degenerative joint disease
- structural defects visible on pre-treatment MRI
 - Any acquired glenoid bone defect
 - Glenoid dysplasia with more than 10° of retroversion (of cartilagineous surface) according to Imhoff et al.⁷
 - Convex cartilagineous glenoid articular surface
 - Static posterior glenohumeral decentering >55% according to Walch et al.¹⁸
 - Degenerative changes (any visible cartilage damage or OA)
- neurological disorder or nerve injury
- existing pain syndrome (defined by pain at rest or during motion which is not caused by dislocation but impedes physiotherapeutic training and/or EMS)
- non-tolerance of EMS treatment (e.g. cardiac pacemaker)
- previous participation in a pathology-specific standardized EMS or physiotherapy protocol for the affected shoulder
- Inability to follow the procedures of the study, e.g. due to language problems, psychological disorders, dementia, etc. of the participant,
- Enrolment of the investigator, his/her family members, employees and other dependent persons

7.2 Recruitment and screening

The estimated prevalence of functional shoulder instability is approximately 0.05% of the population⁵. More precise numbers are not available in the literature. In our pilot trial we treated over 20 cases suffering from FPSI within a one-year timespan at our referral center for shoulder pathologies. All centers included in the proposed project have a similarly large access to potential study participants. Therefore, a sufficient access to the potential study population is available to make recruitment of the planned number of patients within the predefined time period likely. Moreover, the observed acceptance rate of the patients to

participate in a standardized training protocol both, with or without EMS, was very high in the pilot trial. Therefore, the willingness to participate in a randomized trial is expected to be substantial as well, especially considering the offered optional bi-directional cross-over design making both types of intervention accessible for the patients.

During the pilot trial many patients expressed the desire to make this new form of treatment available more close to their home which led us to the decision to turn the proposed project into a multicentric trial involving not only some of the largest shoulder centers in German speaking countries but also considering strategical geographical locations. This should help to reduce time-comsuming travel and costly hotel stays for the patients and their parents and thus facilitate recruitment.

7.3 Criteria for withdrawal / discontinuation of participants

Each patient has the right to withdraw from the study at any time without prejudice. If a subject withdraws from the study, the reason(s) will be stated. Patients who withdraw from the study will not be replaced.

Patient's participation in the study will start by signing and returning the informed consent to the PI or project coordinator. They may end participation prematurely for one of the following reasons: voluntary withdrawal, illness or other event (e.g. complication, trauma event, travel, ...) that prevents further participation in the study and death.

8. STUDY INTERVENTION

8.1 Experimental Intervention (treatment)

The experimental intervention consists of pathology-targeted physiotherapy exercises with simultaneous EMS stimulation which was developed and tested in a pilot trial involving patients without previous treatment success. Electric stimulation targets the external rotators and scapula retractors and consists of rectangular symmetrically compensated alternate current with a frequency of 30Hz and varying intensity. The training involves a combination of pre-defined pathology-targeted exercises with increasing difficulty and intensity. The intervention will include 18 one-hour trainings evenly distributed over a time period of 6 weeks and will be administered by the same physiotherapist at each participating center based on a standardized protocol.

8.2 Control Intervention (standard therapy)

The control intervention consists of the current treatment standard for FPSI, namely pathology-targeted physiotherapy with exercises that were further specified during a Delphi survey. The control intervention will have the same exercises, duration, intervals, and instructing physiotherapist (at each center) as the experimental intervention.

8.3 Crossover

An optional bi-directional cross-over into the other intervention group (experimental or control) is possible after follow-up examination at the time-point T2 (3 months after the beginning/6 weeks after the end of the intervention) in the case of subjectively unsatisfying result despite completion of the originally assigned intervention.

8.4 Compliance with study intervention

The intervention (EMS or physiotherapy) will be logged in the REDCap database to ensure that the patient got the correct intervention. There are no reasons to withdrawn a patient from the study. The patient can drop-out any time from the study. The PI is in charge to collect as much data as possible from withdrawn patients (e.g. telephone call, Email); patients who withdraw from the study will not be examined.

Withdrawn patients will not be replaced.

9. STUDY ASSESSMENTS

9.1 Study flow chart(s) / table of study procedures and assessments

After the patient signed the informed consent they will be allocated in the EMS treatment group or control group by a block randomization procedure.

Each patient (treatment and control group) get a one hour training lesson three times per week during the intervention period of 6 weeks .

The primary endpoint will be measured 3 months after the intervention period has been finished. Afterwards the mentioned optional cross-over in the other group is allowed in the case of subjectively unsatisfying result despite completion of the originally assigned intervention. In this case the study will get one appointment more (4.5 months after patient has been included).

The next time points will be 6 and 12 months after therapy finished.

There will be a measurement of the ROM and different strength parameters at each follow-up appointment (time needed: 30min). Additionally there will be a questionnaire to fill out by the patients to get the subjective parameters (time needed. 30min). Furthermore there will be recorded video from the patient (anonymized; from the backside) to visualize the movement pattern. Optional the patient can hand over a video from his main sport activity (anonymized) to the study coordinator. Both videos will upload into the data base for quality evaluation.

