	- WOSI (Western Ontario Shoulder Instability Index)					
	Secondary Parameter:					
	 SSV (Subjective Shoulder Value) ROM Strength measurement (Flexion/Abduction/Rotation) Impairment of daily activities Sports impairment Pain level Satisfaction level with treatment 					
Study design:	Prospective, randomized, controlled, optional crossover study					

Inclusion / Exclusion criteria:	Key inclusion criteria: - Non-controllable positional functional posterior shoulder instability
	 Key exclusion criteria: < 14 years multidirectional instability static posterior instability/migration connective tissue disease degenerative joint disease structural defects visible on pre-treatment MRI Any acquired glenoid bone defect Glenoid dysplasia with more than 10° of retroversion (of cartilagineous surface) according to Imhoff et al.⁷ Convex cartilagineous glenoid articular surface Static posterior glenohumeral decentering >55% according to Walch et al.¹⁸ Degenerative changes (any visible cartilage damage or OA) neurological disorder or nerve injury existing pain syndrome (defined by pain at rest or during motion which is not caused by dislocation but impedes physiotherapeutic training and/or EMS) non-tolerance of EMS treatment (e.g. cardiac pacemaker) previous participation in a pathology-specific standardized EMS or physiotherapy protocol
Measurements and procedures:	Follow-up per patient (time after start of the treatment) : Baseline (Inclusion), 0 weeks (Start treatment), 6 weeks, 3 months, 6 months and 12 months Duration of intervention per patient : 6 weeks
Study Product / Intervention:	Experimental intervention: electrical muscle stimulation based therapy protocol
Control Intervention (if applicable):	Control intervention : conventional state-of-the art physiotherapy protocol
Number of Participants with Rationale:	There will be a total of 88 patients included. Rationale: See Statistical Considerations
Study Duration:	30 months
Study Schedule:	01/20 First-Participant-In (planned) 07/22 Last-Participant-Out (planned)

Study Centre(s):	It is a multicentric, multi-national study.					
	N=6 clinics					

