	 Clinics: Charitè University Hospital, Berlin, Germany (Leadclinic) ATOS Clinic, Munich, Germany Hannover Medical School (MHH) – DIAKOVERE Annastift – Department of Orthopaedic Surgery, Hannover, Germany St. Vincentius Clinic, Karlsruhe, Germany University Hospital Düsseldorf, Department of Orthopaedics and Trauma Surgery, Düsseldorf, Germany Schulthess Clinic, Zurich, Switzerland 					
Statistical	Sample Size:					
Considerations:	The calculated sample size for a power of 80%, an alpha error probability of 5%, and an estimated effect size of 0,8 is 52. The effect size was calculated according to Cohen by dividing the minimally clinically important difference of the WOSI (10,4%) by the expected standard deviation of the WOSI among the study participants (13%) based on the pilot trial results.					
	When accounting for an expected drop-out rate of approximately 20% due to non-compliance or loss to follow-up 66 patients need to be assigned to the trial. Due to the strict exclusion criteria with an expected exclusion rate of 25% approximately 88 patients need to be assessed for eligibility.					
	In the pilot trial the adherence rate to the EMS treatment was 88%. A similar compliance rate is expected for both intervention groups of the proposed project. The rate of loss to follow-up is expected to be low considering the short follow-up period until reaching the primary endpoint at time-point T2 (3 months after the beginning/6 weeks after the end of the intervention). The expected combined drop-out rate due to lack of compliance with treatment or loss to follow-up is 20%.					
	Primary Analysis					
	The analysis of the primary outcome parameter (WOSI at 3 months) will be performed using an independent sample T-Test or linear regression with WOSI as the dependent variable and treatment intervention and baseline factor(s) as the independent variable depending on the need for statistical adjustment. The strength of effect will be presented as the mean group difference along with its 95% confidence interval. A random-effect model will be used to account for center effect.					
	Secondary Analyses					
	All secondary analyses will be explorative. Secondary outcome variables will be analyzed using univariable random-effect logistic (categorical variables) or linear (continuous variables) regression. Multivariable regression will be conducted depending on the need for adjustment of baseline prognostic factors. Significance level is set to 0.05.					

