6. STUDY DESIGN

6.1 General study design and justification of design

This is a multicentric, prospective, randomized and optional crossover study.

There will be an intervention period of 6 weeks and afterwards a follow up time of totally 12 months. After 3 months the primary endpoint (WOSI) will be measured. Afterwards the mentioned optional cross-over in the other group is allowed in the case of subjectively unsatisfying result despite completion of the originally assigned intervention. This approach ensures that the primary endpoint still can be obtained and only secondary endpoints will be jeopardized if an unexpected high rate of cross-over from one intervention group to the other occurs.

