10.3.2 Primary Analysis

The analysis of the primary outcome parameter (WOSI at 3 months) will be performed using an independent sample T-Test or linear regression with WOSI as the dependent variable and treatment intervention and baseline factor(s) as the independent variable depending on the need for statistical adjustment. The strength of effect will be presented as the mean group difference along with its 95% confidence interval. A random-effect model will be used to account for center effect.

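### Section 9.1 dates the primary endpoint and later visits from the end of treatment, while the synopsis, 3.4 and 8.3 date the primary time point from its start: a six-week contradiction

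*Protocol*

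**What the plan says.** Two clocks are in use.

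**Time from start of treatment.** The synopsis (Measurements and procedures) defines follow-up as "time after start of the treatment" and lists the visits as "Baseline (Inclusion), 0 weeks (Start treatment), 6 weeks, 3 months, 6 months and 12 months". The synopsis (Statistical Considerations) refers to the "primary endpoint at time-point T2 (3 months after the beginning/6 weeks after the end of the intervention". Sections 3.4 and 8.3 use the same T2 as the gate for crossover, which 8.3 describes as "possible after follow-up examination at the time-point T2 (3 months after the beginning/6 weeks after the end of the intervention". Table 1 runs from 0 weeks, with a ±1-week window at 3 months, a ±1-week window at the 4.5-month visit (held only after crossover), and ±2-week windows at 6 and 12 months.

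**Time from end of treatment.** Section 9.1 says "The primary endpoint will be measured 3 months after the intervention period has been finished" and then "The next time points will be 6 and 12 months after therapy finished". Between these sentences it allows crossover after the primary endpoint, and it dates the extra crossover visit 4.5 months from inclusion, which is a third origin.

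**Origin not stated.** Section 6.1 has "After 3 months the primary endpoint (WOSI) will be measured", and section 10.3.2 has "The analysis of the primary outcome parameter (WOSI at 3 months". Neither says what the 3 months are counted from. Section 6.1 also describes 6 weeks of intervention and afterwards a follow-up totalling 12 months, which can be read either way.

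**The concern.** Section 9.1 is the section on study procedures and assessments, so a site may well schedule from it. A site that does so takes the primary WOSI 3 months after treatment. A site working from the synopsis takes it 6 weeks after treatment. These are different quantities, and they would be pooled over six centres under one label, WOSI at 3 months. An analysis plan cannot repair a visit that was held on the wrong date.

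The second issue is crossover. Section 6.1 defends the optional crossover on the ground that the primary endpoint is obtained first, so that only secondary endpoints are put at risk. That holds only if the endpoint date and the crossover opening are counted from the same origin. The discrepancy between the two clocks is 6 weeks, exactly the length of one treatment course.

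**Working it through.** **Inputs.** Intervention: 6 weeks (synopsis, 8.1, 9.1). T2: 3 months after start (synopsis, 3.4, 8.3). Endpoint under 9.1: 3 months after the end of the intervention. Extra crossover visit: 4.5 months (9.1 and Table 1). Windows: ±1 week at 3 months, ±2 weeks at 6 and 12 months (Table 1). Conversion: 1 month = 52.1775/12 = 4.348 weeks.

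**1. The two dates for the primary endpoint, in weeks from start.**
- Synopsis, 3.4, 8.3: 3 × 4.348 = 13.0 weeks.
- Section 9.1: 6 + 13.0 = 19.0 weeks, or 19.0/4.348 = 4.4 months.
- Gap: 19.0 − 13.0 = 6 weeks.

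The protocol itself equates 3 months with 6 + 6 weeks, so 6 weeks counts as 1.5 months. On that rounding the 9.1 date is 3 + 1.5 = 4.5 months.

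**2. Can the window absorb it?** The latest date on the start-based clock is 13.0 + 1 = 14.0 weeks. The earliest on the 9.1 clock, if given the same window, is 19.0 − 1 = 18.0 weeks. The ranges do not meet.

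**3. The later visits.** Under 9.1 they fall at 6 + 6/4.348 = 7.4 months and 12 + 6/4.348 = 13.4 months after start. Each is 6 weeks beyond the Table 1 date, against a window of ±2 weeks.

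**4. Is 9.1 consistent with itself?** Its order is primary endpoint, then crossover, then the extra visit at 4.5 months.
- On its own clock the endpoint is at 19.0 weeks and the extra visit at 4.5 × 4.348 = 19.6 weeks. That leaves 0.6 weeks or less for a 6-week course, because inclusion comes no later than the start of treatment.
- On the start-based clock a course beginning at T2 would end at 13.0 + 6 = 19.0 weeks, and the 19.6-week visit follows it within the ±1-week window.

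The 4.5-month visit therefore fits only if the primary endpoint is at 3 months from start.

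**5. Endpoint and crossover together.**

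| Endpoint date from | Crossover opening from | Endpoint (week) | Crossover opens (week) |
|---|---|---|---|
| Synopsis | 3.4, 8.3 | 13.0 | after the 13.0 visit |
| 9.1 | 9.1 | 19.0 | after the 19.0 visit |
| 9.1 | 3.4, 8.3 | 19.0 | after the 13.0 visit |

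Only in the third row can crossover treatment precede the endpoint. There a patient crossing over at T2 could have completed up to the whole other course (13.0 + 6 = 19.0) when the primary WOSI is taken.

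**6. The sample size.** With d = 10.4/13 = 0.8, two-sided alpha 0.05 and 80% power, the t-test needs 25.5, so 26 per arm and 52 in total, as stated. Dropout gives 52/0.8 = 65 against the stated 66, and screening gives 66/0.75 = 88. None of these depends on the visit date.

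**The case against.** The strongest reply is that this is a drafting slip in one section. The synopsis states the clock explicitly, Table 1 and section 9.2.3 list a 3-month visit, and the 4.5-month visit makes sense only on the start-based clock. Under Table 1 a patient who has not crossed over has no visit at 4.5 months at all. All this stands, and it shows which clock the protocol mainly uses. It does not cancel a sentence in the current version that dates the primary endpoint differently, with a second sentence that moves the later visits the same way.

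A reader might infer that 9.1 by itself puts the primary endpoint after crossover. It does not: it says that crossover comes afterwards. Every section that states an order puts the endpoint first. Contamination needs the endpoint date from 9.1 together with the crossover opening from 3.4 and 8.3.

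A reader might also infer a quantified loss of power. Suppose a share c of controls crosses over and gains the full planned effect before the measurement, so that d becomes 0.80(1 − c). With 26 per arm, power falls from 81% to 72%, 62% or 51% for c = 10%, 20% or 30%. This is a worst case. The protocol gives no crossover rate, crossover is bi-directional but only one direction is modelled, and every site is assumed to mix the sections. If one of six equal-sized sites did so, power would be about 79%, 78% or 77%. The documents support no estimate of this kind, and the point does not rest on one.

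**Conclusion.** The point holds as an internal contradiction about when the primary endpoint is measured. Section 9.1 puts it at about week 19, and the synopsis, with the T2 definition in 3.4 and 8.3, at about week 13. The 6-week difference exceeds the window and equals one course of treatment. The 6- and 12-month visits move by the same amount. The direct consequence is that sites could collect the primary WOSI at different intervals after treatment. Exposure to crossover before the endpoint is conditional on mixing sections, and its effect on power cannot be sized from the protocol. The sample sizes of 52, 66 and 88 are untouched. The dates rest only on the protocol's own intervals and a standard month-to-week conversion. It should be corrected because it fixes what the primary outcome is, and the correction is small.

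**What to change.** Reconcile the assessment dates in section 9.1 with the synopsis, 3.4, 8.3 and Table 1 on one origin, time from start of treatment, with the primary WOSI at T2 before any crossover. Date the 4.5-, 6- and 12-month visits from that same origin. State the origin in 6.1 and 10.3.2 too, where 3 months now stands alone. Check that the REDCap visit schedule uses this date. If primary visits have already been held, check their actual dates against the start of treatment.

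The change concerns when assessments are made and leaves the conditions for crossover as they are. It costs wording in one section, short clarifications in two others and a check of the visit schedule, with no extra patients or visits.

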9.2 Procedures at each visit

9.2.1 Screening day/Baseline:

- Screening of the eligibility of the patients
- Collection of demographic data
- Recording of baseline data
 - Subjective data (Questionnaires)
 - Clinical Examination (ROM and strength measurement)
 - Anonymized video

9.2.2 Intervention visit 1 - 18

Intervention Visits 1 -18 (3 per week; 6 weeks)

- Execution of
 - 1h Intervention: EMS Therapy
 - 1h Control: Physiotherapy
- Acquisition of AEs

9.2.3 FollowUp Visits (6 weeks, 3 months, 4.5 months, 6 months, 12 months)

- Recording of follow-Up data
 - Subjective data (Questionnaires)
 - Clinical Examination (ROM and strength measurement)
 - o Video
- Acquisition of AEs

10. STATISTICAL METHODS

10.1 Hypothesis

Null-Hypothesis:

Electrical muscle stimulation (EMS) based therapy has the same clinical effect as conventional state-of-the art physiotherapy treatment for functional posterior shoulder instability measured by the primary outcome parameter (WOSI Score).

Alternative-Hypothesis:

Electrical muscle stimulation (EMS) based therapy has a better clinical effect as conventional state-of-the art physiotherapy treatment for functional posterior shoulder instability measured by the primary outcome parameter (WOSI Score; MCID Delta > 10,4%).

10.2 Determination of Sample Size

The calculated sample size for a power of 80%, an alpha error probability of 5%, and an estimated effect size of 0,8 is 52. The effect size was calculated according to Cohen by dividing the minimally clinically important difference of the WOSI (10,4%) by the expected standard deviation of the WOSI among the study participants (13%) based on the pilot trial results. The software used to calculate the sample size was G*Power (HHU Duesseldorf, Duesseldorf, Germany). When accounting for an expected drop-out rate of approximately 20% due to non-compliance or loss to follow-up 66 patients need to be assigned to the trial. Due to the strict exclusion criteria with an expected exclusion rate of 25% approximately 88 patients need to be assessed for eligibility.

